2. *Multiple imputation analysis of primary and secondary outcomes.* The results of the mixed effects analyses assume that missing data follow a missing at random (MAR) pattern in which the probability of missingness may depend on other observed outcome values in the model, but are not related to the unobserved values of missing responses themselves. To assess the robustness of our results to bias from missing data, we repeated the mixed effects analyses of the primary and secondary numeric outcomes after multiply imputing missing data using fully sequential imputation under an imputation model that incorporated additional auxiliary variables that were selected using subject matter considerations as potential predictors of the outcomes or the probability of missingness. The multiple imputation models included all variables in the analytic model plus the baseline assessments of gender, age, baseline anxiety, depression, concurrent neck or upper back pain, BMI, length in days of current episode of LBP, and the pain catastrophizing scale, as well as indicator variables for surgery or injections prior to the 4 week and 6 month assessments, and nonmissing longitudinal assessments of the OSW, FABQ physical activity and work subscales, EQ-5D quality of life index, EQ-5D self-rating, and the ratings of low back pain and leg pain in the preceding 24 hours. A total of 25 imputed data sets were created. Results were pooled across these 25 data sets using Rubin's formulae to adjust standard errors to account for variation in results between the imputed data sets in order to account for uncertainty resulting from imputation of missing data.

The sensitivity analyses based on multiple imputation retain a MAR assumption, but the assumption is relaxed to allow dependence of missing outcomes and probability of missingness of the auxiliary variables in the imputation model.

3. *Analyses of utilization outcomes and patient-reported success.* Our main analyses of each of the utilization outcomes – surgery, lumbar epidural injection, advanced imaging and emergency department visits - were performed by calculating relative risk statistics and 95% confidence intervals.

We used relative risk rather than Cox regression in our main analyses of each utilization outcome because these outcomes generally occurred early in follow-up and we did not view the timing of the outcome events as highly clinically relevant. In order to assess the dependence of

the results to early dropout and missing assessments, we repeated our analyses of each of the utilization outcomes using Cox regression analysis to relate the outcome to the randomized treatment assignment, with follow-up censored at the final monthly utilization assessment. The Cox regression analyses were performed using a counting process style input in which intermittently missing monthly assessments were excluded from the risk set.

We applied separate analyses of relative risk to relate patient-reported success at the 4 week, 6 month and 1 year assessments to the randomized treatment assignment.

4. *Analyses of missed work days.* We used a generalized estimating equations (GEE) analysis with robust standard errors under a negative binomial outcome model with logarithmic link function to compare the number of missed work days due to LBP per month over the 1 year follow-up period between the randomized groups. The GEE analysis was performed using a compound symmetry working covariance matrix to account for serial correlation over the monthly assessments during the follow-up period. The model included randomized treatment assignment and follow-up month coded as a categorical factor as predictor variables.

A separate GEE analysis used a Bernoulli outcome model with logarithmic link to compare the proportion of patients missing at least one work day in a given month between the randomized treatment groups. This analysis also used a compound symmetry working covariance model and robust standard errors for statistical inference.

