Healthcare Utilization and Direct and Indirect Costs: [*We will collect both direct and indirect costs due to lost work productivity related to LBP over the 1-year follow-up.*] We will use a cost diary method integrated into the web-based data collection system to collect utilization and cost data. Cost diaries offer advantages in terms of feasibility and validity as compared with patient-reported questionnaires for collecting cost data and provide information at regular intervals instead of relying on patient recall over a long time period, minimizing recall error.¹⁰⁹ [*We will collect cost and utilization data monthly via REDCap using the input options outlined below.*] The cost diary will be modeled on paper-based methods with high compliance (85%) for economic analysis in studies of patients with LBP.^{108,131} This compliance rate is consistent with our experience using this method in our ongoing study. Prior research reports no differences between cost

diaries completed for an entire year and extrapolation of data for limited time periods, indicating a robustness to impute scores for random missing data. Patient-reported cost diary data has been found to generally agree with insurance claims, supporting the validity of the self-report cost and utilization data.¹⁰⁸ [*Each monthly cost diary will ask patients if they have utilized healthcare resources in the past month specifically for LBP in 4 categories: 1) provider visits (traditional or complementary/alternative), 2) medications (prescription or over-the-counter), 3) interventions (injections, surgery, etc.), or testing (x-rays, MRI, etc.), and 4) lost time from work or decreased work productivity. Conditional logic will be used to reduce response burden for patients not seeking any care. Patients who are seeking care will be given follow-up questions to ascertain the number and nature of utilization in each category in the past month.]*

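### Procedures that fall in a skipped diary month are never recovered; the main relative risk bears most of the loss, and the Cox check corrects it only if skipping is unrelated to events

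*SAP*

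**What the plan says.** Protocol C.5 (Healthcare Utilization and Direct and Indirect Costs) makes the patient's web diary the source of utilization data: "We will collect cost and utilization data monthly via REDCap". The recall window is one month: "Each monthly cost diary will ask patients if they have utilized healthcare resources in the past month specifically for LBP". The same paragraph cites 85% compliance for the paper diaries on which this one is modelled and says that the team's ongoing study is consistent with it.

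SAP item 3 gives the analysis. The main analyses of surgery, epidural injection, advanced imaging and emergency visits "were performed by calculating relative risk statistics and 95% confidence intervals". Cox regression is the repeat analysis, and incomplete follow-up is the reason given for it: "the results to early dropout and missing assessments, we repeated our analyses of each of the utilization outcomes using Cox regression analysis". It runs "with follow-up censored at the final monthly utilization assessment", and within that span "intermittently missing monthly assessments were excluded from the risk set".

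Neither document describes a look-back question after a missed diary, a records or claims check of these outcomes, or imputation of them. Protocol C.9 promises multiple imputation for missing outcome data in general. SAP item 2 applies it to the numeric outcomes, and the Aim 2 text of C.9 applies it to costs. SAP item 3 does not mention it.

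**The concern.** A question about the past month cannot pick up a procedure from a month whose diary was not returned. The patient's next diary can truthfully report nothing, and the procedure is absent from the data for both analyses.

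Reduced use of MRI and injections is the Aim 2 hypothesis. Two things are at stake. Lost events cost precision whatever the cause of skipping. In addition, patients know their treatment, so completion could differ by arm; a patient having surgery or an emergency visit could also be less likely to complete that month's diary. The first can distort the relative risk. Both together can distort the Cox result too, although Cox is the analysis meant to show whether missing assessments matter.

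**Working it through.** **The plan's own figures.** The documents give no event rate, event count or power for utilization. The power figures in Protocol C.11 concern OSW and NPRS and play no part here, though the main one reproduces (99 per arm, difference 7, SD 16: 86.8%, against at least 86% stated).

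**Inputs.** From the documents: 110 per arm, two-sided alpha 0.05, one-month recall, skipped months removed in Cox. Assumed: annual risks (20% in UC, and 10% or 20% in EPT), completion by arm, one event per patient, and a patient with no reported event counted as having none in the relative risk.

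**1. How common gaps could be.** If 85% applied independently to each month, 1 − 0.85^12 = 86% of patients would miss at least one diary, and about 15% of single events would fall in missed months.

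**2. Relative risk, no true effect, skipping unrelated to events.** The expected RR is the ratio of completion rates.
- 90% EPT, 80% UC: 0.90/0.80 = 1.125.
- 88% EPT, 82% UC: 0.88/0.82 = 1.07.

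**3. Power with equal 15% loss.** Power = Φ[(d − 1.96·SE0)/SE1], with SE0 pooled and SE1 unpooled.
- 20% versus 10%: d = 0.10, SE0 = 0.0481, SE1 = 0.0477, power 54.7%.
- 17% versus 8.5%: d = 0.085, SE0 = 0.0450, SE1 = 0.0446, power 47.2%.

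**4. Cox, same skipping as in step 2 (90% versus 80%).** Each arm's observed rate is proportional to its share of events captured divided by its share of time observed. EPT: 0.90/0.90 = 1. UC: 0.80/0.80 = 1. Ratio 1.00. Patients whose event was lost return to the risk set, slightly more often in UC, which moves the ratio a little. A full month-by-month calculation (Mantel-Haenszel rate ratio over 12 months, 20% risk, events weighted to early months) gives HR 1.01. Across risks of 10% to 30%, with events early or uniform, the range is 1.004 to 1.017.

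**5. Cox, event months twice as likely to be skipped.** Skipping is 10% EPT and 20% UC, so 20% and 40% of events are lost.
- RR, no effect: 0.80/0.60 = 1.33.
- HR, no effect, first approximation: (0.80/0.90)/(0.60/0.80) = 0.889/0.75 = 1.19. The month-by-month calculation gives 1.20.

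**6. Summary with a true effect (20% UC, 10% EPT; true RR 0.50, HR 0.48).**

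| Months skipped, UC / EPT | Event months | Events lost, UC / EPT | RR | HR |
|---|---|---|---|---|
| 15% / 15% | same as others | 15% / 15% | 0.50 | 0.48 |
| 20% / 10% | same as others | 20% / 10% | 0.56 | 0.48 |
| 15% / 15% | twice as likely | 30% / 30% | 0.50 | 0.48 |
| 20% / 10% | twice as likely | 40% / 20% | 0.67 | 0.58 |

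Events are lost in every row. The RR moves whenever skipping differs by arm. The HR moves materially only in the last row.

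**The case against.** The strongest reply is that the Cox analysis does much of its job. Removing a skipped month removes its event and its person-time together, so differing completion largely cancels. Step 4 bears this out. A reader might infer that the Cox check simply repeats the error and could never reveal it. The documents do not support that reading: with skipping unrelated to events, an RR of 1.125 beside an HR near 1.01 is the gap that would expose the artefact. Nor is the patient counted as event-free during the skipped month. Misclassification starts on re-entry, and only if no other event of that type is reported. The SAP does not say whether the model is first-event or repeated-event. Protocol C.9 plans repeated-event methods, for which dropping an unobserved interval is acceptable if skipping is unrelated to events.

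Three further points deserve weight. The diary forms are in an appendix that is not in the documents, so the lack of a look-back item is inferred from the text of C.5. Protocol C.6 has off-protocol interventions identified at the 4-week visit, and the SAP notes that "these outcomes generally occurred early in follow-up". SAP item 2 uses surgery and injection indicators whose source is not given. Either could mean that some events were recovered. But the 4-week check is described for treatment fidelity and covers only the first month, and neither source is linked to the utilization outcomes.

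Finally, the SAP reports completed work in the past tense, so a new diary question cannot repair data already collected. That changes the remedy, not the gap.

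**Conclusion.** The concern holds as a gap in event capture that falls mainly on the main relative-risk analysis. Under the plan as described, procedures in skipped months are missing from both analyses. Under the assumed rates, an equal 15% loss costs about 7 to 8 points of power (54.7% to 47.2%), and 90% versus 80% completion alone gives an RR of 1.125 with no true effect.

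The Cox analysis is a partial check. It is nearly unbiased when skipping is unrelated to events, but it restores no lost event, and it rests on that very condition. When skipping is event-related and also differs by arm, it errs in the same direction as the RR (HR about 1.20 and RR 1.33 under no effect), and agreement between the two would give false reassurance.

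All sizes depend on assumed event risks, arm differences and skipping patterns. The 85% comes from other diary studies and is not defined as independent monthly completion. If skipped months were in fact recovered from another source, a sentence saying so would settle the point.

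**What to change.** **In the protocol's data collection.** Have each monthly diary, and the 6-month and 1-year online forms, ask about the four procedures since the last completed diary. Count recovered events in the relative risk. In the Cox analysis, place a recovered event in the gap or treat it as interval-censored, so that the patient does not re-enter as event-free. State whether the model is first-event or repeated-event.

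**Where data were already collected without look-back.** Say whether any other source filled skipped months. Report diary completion by arm. Add a sensitivity analysis that imputes events in skipped months, first with skipping unrelated to events and then with event months more likely to be skipped, including differently by arm.

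**Cost.** One conditional question and a small coding change for the first part; one table and one added analysis for the second. The downside of the look-back is longer recall for patients who skipped, limited to four salient events.
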